7.2 Sample Size Determination

For the primary safety outcomes, we consider the expected upper limit of a one-sided 90% exact confidence interval for the proportion with an SAE based on a sample size of 20. If the underlying rate is 0.05, the upper limit is 0.131. This increases to 0.145 if the underlying rate is 0.10.

For the secondary outcomes comparing baseline to endpoint depression measurements, a two-sided paired t-test with a significance level of 0.05 and a power of 0.90 can detect a difference of .764 standard deviations of the changes from baseline.

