7.1 Statistical Methods

The study will be closely monitored for safety parameters with stopping rules as defined in Section 8.7. At the conclusion of the study, baseline demographics and clinical characteristics will be summarized with means, proportions and associated standard deviations. For safety, occurrence rates of SAE (seizures or hospitalizations) will be estimated and exact binomial confidence intervals will be formed. Very few if any are expected in this small study. The SAFTEE scale will be compared before and after TMS with independent t-tests based on the individual changes from baseline. The study completion rates will be estimated and compared to the target rate of 80% using exact tests for binomial data.

The secondary outcomes will be measured before and after treatment using dense-array EEG biomarkers and depression scores along with test results during functional MRI and EEG. Paired t-tests will be used to compare *change* in depression severity, memory, executive functioning, quality of life, and social cognition from baseline to endpoint. MRI patterns of activation will be analyzed. Analysis of variance for repeated measures will be used to test task and neuropsychological testing results.

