8.7 Stopping Rules

Study safety will be monitored by the co-PIs .The study will be stopped at if the following endpoints are reached:

1. If recruitment for the study is not feasible
 - a. no recruitment after 1 year
 - b. > 4 drop outs due to any reason (80% feasibility)
2. If TMS is deemed unsafe to patients with epilepsy

- a. > 3 patients with increase in baseline seizure frequency
- b. > 3 patients with significant worsening of depression
- c. > 3 patients with significant side effects of TMS other than seizures

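### Section 7.2 understates the expected upper limits for the SAE rate: with 20 patients they are 0.177 and 0.241, not 0.131 and 0.145

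*Combined protocol and SAP*

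**What the plan says.** Section 7.2 (Sample Size Determination) names the quantity used to judge precision for the primary safety outcomes: the "expected upper limit of a one-sided 90% exact confidence interval for the proportion with an SAE based on a sample size of 20". It then gives two values: "If the underlying rate is 0.05, the upper limit is 0.131. This increases to 0.145 if the underlying rate is 0.10".

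Section 7.1 (Statistical Methods) plans the matching analysis. SAE rates, with SAEs taken as seizures or hospitalizations, will be estimated, and "exact binomial confidence intervals will be formed. Very few if any are expected in this small study".

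No other section defines the two limits differently or sets a maximum acceptable limit. The stopping rules in section 8.7 are counts of patients, for example "> 3 patients with increase in baseline seizure frequency".

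**The concern.** The two values look implausible before any calculation. When the underlying rate rises by 0.05, the stated limit rises by only 0.014 (0.145 − 0.131). At a rate of 0.10 with 20 patients, a limit of 0.145 would lie only 0.045 above the rate, which is very tight for an exact 90% bound.

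These are the only precision figures offered for the primary safety outcome. An IRB member or reader who asks what 20 patients can show about SAEs would conclude from section 7.2 that a rate of 15% is expected to be excluded under either scenario. If the limits are really about 18% and 24%, that conclusion is wrong, and wrong in the reassuring direction.

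**Working it through.** **Inputs, all from section 7.2.** n = 20; exact interval, one-sided, 90%; underlying rates 0.05 and 0.10. Nothing has to be assumed beyond reading exact as Clopper-Pearson.

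**Formula.** With x SAEs among 20 patients, the upper limit U(x) solves P(X ≤ x | n = 20, U) = 0.10. Equivalently, U(x) is the 0.90 quantile of a Beta(x + 1, 20 − x) distribution.

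| SAEs observed | U(x) |
|---|---|
| 0 | 0.10875 |
| 1 | 0.18096 |
| 2 | 0.24477 |
| 3 | 0.30419 |
| 4 | 0.36066 |

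The zero-event value can be checked by hand: 1 − 0.10^(1/20) = 0.1087.

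**Reading 1: expected limit, as the text says.** E[U] = Σ P(X = x) · U(x), with X ~ Binomial(20, p).

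| x | P(X = x), p = 0.05 | product | P(X = x), p = 0.10 | product |
|---|---|---|---|---|
| 0 | 0.35849 | 0.03899 | 0.12158 | 0.01322 |
| 1 | 0.37735 | 0.06829 | 0.27017 | 0.04889 |
| 2 | 0.18868 | 0.04618 | 0.28518 | 0.06980 |
| 3 | 0.05958 | 0.01812 | 0.19012 | 0.05783 |
| 4 | 0.01333 | 0.00481 | 0.08978 | 0.03238 |
| 5 or more | | 0.00109 | | 0.01865 |
| **Sum** | | **0.1775** | | **0.2408** |

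The expected limits are 0.177 and 0.241.

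**Reading 2: limit when the observed proportion equals the rate.** 20 × 0.05 = 1 SAE gives 0.181. 20 × 0.10 = 2 SAEs gives 0.245.

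**Attempt to reproduce the plan's figures.** Clopper-Pearson, Wald, Wilson and Jeffreys limits were tried at one-sided 80%, 90%, 95% and 97.5%, both at x = np and in expectation. None gives both 0.131 and 0.145. The nearest partial match is a one-sided 95% Wald limit at 0.05 (0.130), but that method gives 0.210 at 0.10. Both stated figures do match limit minus proportion under reading 2:

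- 0.18096 − 0.05 = 0.13096, stated as 0.131
- 0.24477 − 0.10 = 0.14477, stated as 0.145

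The same subtraction under reading 1 gives 0.127 and 0.141, which do not match.

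**What the stated figures deliver if used as limits.** P(X ≤ 1 | 20, 0.131) = 0.242, so 0.131 with 1 SAE has 75.8% confidence. P(X ≤ 2 | 20, 0.145) = 0.430, so 0.145 with 2 SAEs has 57.0%. Both should be 90%.

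**How often it matters.** Only with no SAE does the limit (0.109) fall below the stated figures. From 1 SAE upward it is at least 0.181, above both. The chance of 1 or more SAEs is 1 − 0.95^20 = 0.642 at a rate of 0.05 and 1 − 0.90^20 = 0.878 at 0.10.

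**Neighbouring figure.** The other number in section 7.2, the detectable difference of 0.764 SD for the paired t-test, reproduces with n = 20 (0.7645 by the noncentral t). The fault is confined to the two SAE limits.

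**The case against.** The strongest reply is that nothing in the trial depends on these numbers. Section 7.2 sets no threshold for the limit, so N = 20 is not derived from them. Section 7.1 computes the exact intervals from the observed data, section 8.7 stops on patient counts, and section 3.1 describes a pilot study. All of this is correct, and it confines the consequence to how a reader or IRB judges the planned precision. That judgement is the purpose of a precision statement, however, and no other figure is offered for it.

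A second reply is that the numbers may be right and only the label wrong: as distances from the observed proportion to its limit, they are correct. That is probably what happened, but section 7.2 calls the quantity an upper limit both when it defines it and when it gives the first value. A reader cannot recover the other meaning from the text.

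A third reply is that few or no SAEs are expected, and with none the limit is 0.109, better than either stated figure. This holds for that one outcome. Under the plan's own two rates it has probability 0.358 and 0.122. Those rates are illustrations, not forecasts, so the probabilities carry no more weight than the rates do.

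**Conclusion.** The concern holds. As labelled, both figures are wrong, and both are too favourable. On the literal reading they understate the expected limit by 0.046 at a rate of 0.05 (0.131 against 0.177) and by 0.096 at 0.10 (0.145 against 0.241). On the observed-count reading the shortfalls are 0.050 (0.131 against 0.181) and 0.100 (0.145 against 0.245). The result rests only on the inputs that section 7.2 states and on Clopper-Pearson as the exact method. That a distance was reported in place of a limit is an inference from the match to three decimals. The error does not depend on that inference.

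**What to change.** In section 7.2, replace 0.131 and 0.145 by one correctly labelled pair:

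- 0.177 and 0.241, as the expected upper limits at underlying rates 0.05 and 0.10. This fits the present wording.
- 0.181 and 0.245, as the upper limits when 1 and 2 of 20 patients have an SAE. This is closest to what seems to have been calculated, and the word expected should then be dropped.

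Add that the limit with no SAE is 0.109. If the authors prefer to keep 0.131 and 0.145, they must describe them as the distance from an observed proportion of 1/20 or 2/20 to its upper limit, not as limits; giving the limits beside them would be clearer.

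The cost is two numbers and a clause. The stated precision becomes less favourable. N, the analysis and the stopping rules do not change.

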7.3 Subject Population(s) for Analysis

The patients successfully initiating the trial will be the analysis population to the safety outcomes. The patients completing the TMS will be the population for the secondary outcomes.

8 Safety and Adverse Events

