4.2.1 When and How to Discontinue Treatment

Treatment will be discontinued and the subject may be withdrawn from the study prior to completion due to any of the following reasons:

1. The subject experiences greater than 3 typical seizures during the 3 day course of TMS treatment or they experience a single atypical seizure (atypical duration or severity for the patient) as judged by study neurologist.
2. The subject experiences a worsening of depressive symptoms by the discretion of the study psychiatrist.
3. The subject withdraws consent.
4. The subject is not able to tolerate TMS (as assessed by self-reported side effects).
5. The subject does not adhere to protocol requirements.

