4.3.2 Data Collection and Follow-up for Withdrawn Subjects

Should a subject be withdrawn prematurely from the study, follow-up will continue to be attempted as planned based on protocol: subjects will complete assessments immediately following discontinuation of TMS, one week after last TMS treatment, one month after last TMS treatment, and three months after last TMS treatment. For a subject to be considered “lost to follow-up,” they must at a minimum fail to respond to 3 consecutive attempts at communications from study team (email and phone contact). Follow-up will not occur if a subject refuses to participate in follow-up assessments.

5 Study Device

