6.1 Visit 1a: Initial Screening by Neurologist – Pre-enrollment

- Patient will review and sign informed consent.
- Initial screening will be done by a board-certified neurologist (, Visit 1a). Patient's history and physical will be taken, medications will be reviewed, seizure log, MOCA will be performed if time permits. All incomplete assessments may be done at Visit 1b.
- Subject will receive seizure log and instructions for its use.

6.2 *Visit 1b: Initial Screening by Psychiatrist – Pre-enrollment*

- Subsequent evaluation will be done by board-certified psychiatrist and research assistant Visit 1b). If the subject is unable to complete the full screening during Visit 1a, he or she may be scheduled for a second screening appointment with study psychiatrist and research assistant. At that time, diagnosis of medication-resistant depression will be confirmed; the MINI, QIDS, SAFTEE, PANAS MRI safety, TASS and ATHF will be performed. Seizure log data will be obtained.
- If time permits, Visit 2 procedures can be done at Visit 1b.

6.3 *Visit 2: Imaging and Baseline Neuropsychological Testing – Pre Enrollment*

- Patient will be report to the Advanced Imaging Center for MRI. MRI will last approximately one hour.
- After MRI is complete, patient will be brought to the EEG lab . A dense-array EEG will be conducted which will take approximately one hour.
- Patient will do neuropsychological and social-cognition testing, which will last approximately 2 hours. (QOLIE-31, RBANS and MAC-S)
- If time permits, TMS motor threshold may be done at Visit 2, so long as TMS treatment is scheduled to begin within one week. Otherwise, TMS motor threshold will be done at Visit 3.

6.4 *Visit 3: Enrollment and first day of TMS treatment*

- Patient will be brought to DHMC by their proxy for the first day of TMS treatment.
- Research staff will administer the QIDS, SAFTEE, and PANAS. Data will be obtained from the patient's seizure log.

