- Patient will be given TMS motor threshold test to calibrate the machine for treatment, if not done at Visit 2. Following calibration, the designated TMS trained study team member or study RN will begin administering the first TMS treatment session under supervision of the study psychiatrist . Each treatment session will last approximately 50 minutes, and the patient will be given the opportunity to take a break between sessions. The patient will be scheduled to receive four, and may receive as many as seven, treatment sessions by the end of Visit 3.
- Following the final TMS session, study personnel will administer the SAFTEE, and PANAS.
- Following TMS, the family member/proxy will be instructed how to monitor the patient for safety, and he or she will be given contact information in case of unusually strong seizures. A hotel room will have been booked by study personnel prior to the study visit, if needed. The proxy will stay in the same room as the patient between all treatment days.
- The study Neurologist will be on call in case of unusual seizures.
-

6.5 *Visit 4: Second day of treatment*

- The proxy will bring the patient back to DHMC, and report to the Psychiatry Clinic for Visit 4.
- Research staff will administer the SAFTEE and PANAS. Seizure log will be reviewed.
- After completing assessments, the subject will begin the planned seven treatment sessions. Break times will be provided between sessions if desired.
- At the end of the final treatment session, research staff will:
 - Administer the SAFTEE and PANAS.
 - Remind the patient and proxy about contact and safety information before they depart.
- The study Neurologist will remain on call in case of unusually strong seizures.

6.6 *Visit 5: Third day of treatment*

- The proxy will bring the patient back to the Psychiatry Clinic for Visit 5.
- Research staff will administer the SAFTEE, PANAS. Seizure log will be reviewed.
- The patient will have four planned treatment sessions, but may receive as many as seven treatment sessions, with the opportunity to rest between trains.
- Once the final TMS treatment session is complete, a second dense-array EEG test will be conducted, which will last approximately one hour.
- After completion of the dense-array EEG, research staff will:
 - Administer the SAFTEE, PANAS, QIDS, and MoCA.
 - Debrief patient and proxy. Provide with safety information.
- Patient will be taken home by proxy*.

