6.8 Visit 7: 1-month follow up

- 1 month after visit 5 (+/- 2 weeks), the patient will return to DHMC for a follow up with the study neurologist for history and physical, and medication review. Seizure log will be reviewed.
- The patient will have the SAFTEE, QIDS, and MoCA administered by research staff.
- Neuropsychological testing (QOLIE-31, MAC-S, RBANS),
- Dense-array EEG test will be conducted.

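### Section 7.3 restricts depression change to TMS completers, although TMS can be stopped for worsening depression; if such stops track the endpoint score, the uncontrolled mean change shifts toward benefit, probably slightly

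*Combined protocol and SAP*

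**What the plan says.** Section 7.3 uses two analysis sets. Safety outcomes use everyone who starts the trial. For the rest: "The patients completing the TMS will be the population for the secondary outcomes".

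Sections 7.1 and 7.2 place depression change among those secondary outcomes. Section 7.1 plans paired t-tests of change in "depression severity, memory, executive functioning, quality of life, and social cognition from baseline to endpoint", and Section 7.2 says that the depression comparison, two-sided at 0.05 with 90% power, "can detect a difference of .764 standard deviations of the changes from baseline". The study summary describes a non-randomized study without controls.

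Among the reasons for stopping treatment, Section 4.2.1 lists: "The subject experiences a worsening of depressive symptoms by the discretion of the study psychiatrist". For subjects withdrawn early, Section 4.3.2 plans attempted assessments immediately after TMS is discontinued and then "one week after last TMS treatment, one month after last TMS treatment, and three months after last TMS treatment", unless the subject refuses. It lists no 6-month assessment, whereas Section 6.10 has a 6-month Visit 9.

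The text provided does not tie the word endpoint to a visit. QIDS is scheduled after treatment at Visits 5, 6, 7, 8 and 9. No all-treated analysis, sensitivity analysis or missing-data rule appears for these outcomes.

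**The concern.** A clinical judgement about depression can decide who enters the analysis of depression. A patient whose mood worsens during the treatment days may be stopped, is then not a TMS completer, and drops out of the mean change, even if the later QIDS scores that Section 4.3.2 tries to collect are on file. If those scores tend to be worse than average, the remaining mean looks better than the mean for everyone treated.

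With no control group, this pre-post change is the study's only estimate of improvement, and no second arm exists in which the same selection might partly cancel. Neither specific aim tests mean improvement, but Section 7.1 plans the test and Section 7.2 powers it. What is at stake is therefore the size of a reported secondary result in a 20-patient pilot.

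**Working it through.** **1. The plan's own figure.** Inputs from Section 7.2: two-sided α = 0.05, power 0.90, paired t-test; N = 20 comes from the safety paragraph of the same section. Power is computed from the noncentral t distribution with n − 1 degrees of freedom and noncentrality d√n. At n = 20, 90% power gives d = 0.7645, and power at 0.764 is 0.900. The stated 0.764 SD reproduces for 20 analysed patients. With fewer:

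| Analysed | Detectable at 90% power (SD) | Power at 0.764 SD |
|---|---|---|
| 20 | 0.764 | 90% |
| 19 | 0.787 | 88% |
| 18 | 0.811 | 86% |
| 17 | 0.838 | 84% |
| 16 | 0.868 | 81% |

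The power loss from a few exclusions is modest. The selection is the main point.

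**2. Size of the shift under Section 7.3.** The number stopped for worsening (k) and the correlation (ρ) between the stopping judgement and the endpoint change are not in the documents, so both are assumptions. I take k = 1, 2 or 3 as illustrative. Section 8.7, rule 2b, stops the study above 3 significantly worsened patients, but it does not count TMS stops, so it sets no strict ceiling on k.

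Model: 20 standardized changes with true mean 0 (positive = worse). Each patient has a stopping score L, and change = ρL + √(1 − ρ²)e, with L and e independent standard normals. The k patients with the highest L are removed.

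Expected mean of those left = −ρ × S_k / (20 − k), where S_k is the sum of the k largest expected values among 20 standard normals (1.87, 1.41, 1.13):

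- k = 1: 1.87/19 = 0.098
- k = 2: (1.87 + 1.41)/18 = 0.182
- k = 3: (1.87 + 1.41 + 1.13)/17 = 0.259

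Multiplying by ρ gives the shift. The chance of a significant improvement when there is none comes from simulation (300,000 trials, two-sided 0.05 t-test; nominal 2.5% in the benefit direction):

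| ρ | Shift toward benefit, k = 1 / 2 / 3 (SD) | False improvement, k = 1 / 2 / 3 |
|---|---|---|
| 0 | 0 / 0 / 0 | 2.5% throughout |
| 0.3 | 0.03 / 0.05 / 0.08 | 3.4% / 4.2% / 5.0% |
| 0.5 | 0.05 / 0.09 / 0.13 | 4.2% / 6.0% / 8.1% |
| 1.0 (upper bound) | 0.10 / 0.18 / 0.26 | 7.5% / 15.5% / 25.8% |

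The largest shift at ρ = 0.5 is 0.131/0.764 = 17% of the detectable difference. The last row needs perfect selection and is only a bound.

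**3. What an all-treated set recovers, at ρ = 0.5.** If every stopped patient's endpoint value is obtained, the shift is 0 and the rate 2.5%. With 3 stopped and 1 value missing at random among them: 0.04 SD and 3.7%. With 3 stopped and 2 missing: 0.08 SD and 5.4%. As written, with all 3 excluded: 0.13 SD and 8.1%.

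**4. Which visits could serve as the endpoint.** The times in Section 4.3.2, set against the visit schedule in Section 6:

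| Time | Scheduled |
|---|---|
| End of TMS (Visit 5) | QIDS, PANAS, SAFTEE, MoCA, EEG |
| 1 week (Visit 6) | QIDS, SAFTEE |
| 1 month (Visit 7) | QIDS, SAFTEE, MoCA, QOLIE-31, MAC-S, RBANS, EEG; no PANAS or fMRI |
| 3 months (Visit 8) | QIDS, SAFTEE |
| 6 months (Visit 9) | QIDS and neuropsychological tests, but not listed in 4.3.2 |

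Of the times planned for stopped patients, 1 month is the only one with QIDS, QOLIE-31, MAC-S, RBANS and EEG together. Section 6.8 says of that visit: "The patient will have the SAFTEE, QIDS, and MoCA administered by research staff".

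**The case against.** The strongest reply is that the bias may never arise. TMS runs over 3 days, 4 at most (Section 5.1), so few stops for worsening mood are likely, and worsening after the last session leaves the patient in the completer set. The link between a stop and a later score could be weak: QIDS covers the past seven days, and Section 5.4 allows medication changes when medically necessary, so a 1-month score may reflect other treatment. One stop at correlation 0.3 moves the mean by only 0.03 SD. The study is a pilot on safety, feasibility and biomarkers; an uncontrolled change cannot establish efficacy in either population, and completers can be a legitimate population of interest. All of this stands and limits the weight of the point. It does not explain why scores that the protocol tries to collect should be left out of the main estimate.

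A reader might infer that the plan hides patients who get worse. It does not: safety outcomes use everyone who starts, and rule 2b in Section 8.7 counts significant worsening of depression. A reader might also infer that 0.764 SD is an error. It is correct for 20 analysed. Nor can it be said that the endpoint visit is defined nowhere, because Table 1, the Study Visit Guide and the Study Procedures Table are not reproduced in the text available.

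**Conclusion.** The point holds conditionally. Section 7.3 lets an outcome-related stop remove a patient from the depression analysis, while Section 4.3.2 plans to seek that patient's scores. Bias from this source needs at least one stop for worsening and a correlation between that judgement and the endpoint score. Without both there is none, so the documents do not support saying that the depression result will be biased.

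Under the assumed scenarios the shift is 0.03 to 0.13 SD, with false improvement between about 3% and 8% instead of 2.5%. These figures rest on assumed counts of 1 to 3, assumed correlations of 0.3 and 0.5, and normally distributed changes. The effect is probably small. The change is worth making because it is cheap and removes an avoidable selection from the only estimate of improvement. The unnamed endpoint visit and the missing N for the depression calculation are details that matter mainly because the repair depends on them.

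**What to change.** - **Section 7.3.** Make the main set for depression change all patients who received any TMS and have both a baseline value and a value at the named endpoint visit, whether or not they completed TMS. Do not carry an earlier score forward. Report how many stopped patients lack the endpoint value and why they stopped. Apply the same rule to the other questionnaire and neuropsychological outcomes where the endpoint value exists. Keep the paired t-test and give TMS completers as a sensitivity analysis.
- **Section 7.1.** If the attachments do not already do so, name an endpoint visit that Section 4.3.2 also lists. It may differ by outcome: 1 month suits QIDS with QOLIE-31, MAC-S and RBANS, and the EEG-depression correlation may use Visit 5. If 6 months is meant, Section 4.3.2 and Visit 9 must be reconciled.
- **Section 7.2 (optional).** State that 0.764 SD is for 20 analysed, and give 0.787, 0.811, 0.838 and 0.868 SD for 19, 18, 17 and 16.

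The cost is wording, with the same test and no added assessment if the endpoint is a time that Section 4.3.2 already lists. The estimate may come out less favourable, and missing values among stopped patients can leave part of the shift in place.
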